# 9 PHARMACOVIGILANCE

#### 9.1 Definitions

Term	Definition
Adverse Event (AE)	Any untoward medical occurrence in a participant to whom a medicinal product has been administered, including occurrences which are not necessarily caused by or related to that product.
Adverse Reaction (AR)	An untoward and unintended response in a participant to an investigational medicinal product which is related to any dose administered to that participant.
	The phrase "response to an investigational medicinal product" means that a causal relationship between a trial medication and an AE is at least a reasonable possibility, i.e. the relationship cannot be ruled out.
	All cases judged by either the reporting medically qualified professional or the Sponsor as having a reasonable suspected causal relationship to the trial medication qualify as adverse reactions.
Serious Adverse Event (SAE)	
 
A serious adverse event is any untoward medical occurrence that:
 
results in death
 
is life-threatening
 
requires inpatient hospitalisation or prolongation of existing hospitalisation
 
results in persistent or significant disability/incapacity
 
consists of a congenital anomaly or birth defect
 
Other 'important medical events' may also be considered serious if they jeopardise the participant or require an intervention to prevent one of the above consequences.
 
NOTE: The term "life-threatening" in the definition of "serious" refers to an event in which the participant was at risk of death at the time of the event; it does not refer to an event which hypothetically might have caused death if it were more severe.
 

Serious Adverse Reaction (SAR)	An adverse event that is both serious and, in the opinion of the reporting Investigator, believed with reasonable probability to be due to one of the trial treatments, based on the information provided.
Suspected Unexpected Serious Adverse Reaction (SUSAR)	
 
A serious adverse reaction, the nature and severity of which is not consistent with the information about the medicinal product in question set out:
 
in the case of a product with a marketing authorisation, in the summary of product characteristics MHRA approved (SmPC) for that product
 
in the case of any other investigational medicinal product, in the investigator's brochure (IB) relating to the trial in question
 

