	dizziness, fatigue, flushing, irritability, headache, loss of appetite, nausea, vomiting, taste disturbance, paraesthesia.	
	Severe hyperchloraemia 107-110 mmol/L	
Serious Adverse	Severe metabolic acidosis bicarbonate <20 mmol/L	
Reactions	Any of the possible side effects of acetazolamide listed in the MHRA	
	approved SPC that are intolerable to the patient and lead to	
	investigations.	
Suspected Unexpected Serious Adverse Reactions	Any SAR that is not expected based on the MHRA SPC for acetazolamide in relation to the nature and severity of the SAR will be reported as SUSAR. Due to the lack of data on the safety and tolerability of acetazolamide in modern patients with heart failure treated with high dose loop diuretic we will consider any SAR that occurs in >5% of patients as a SUSAR	

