# 9.4 Reporting of SAEs AND SUSARs

All SAEs, SARS and SUSARs (except those defined as not requiring expedited reporting) will be reported to the Sponsor using the study specific SAE report form, within 24 hours of the research staff becoming aware of the event.

For each reported SAE the following information will be collected:

- full details in medical terms and case description
- event duration (start and end dates, if applicable, and if admitted, admission and discharge dates, with specialty noted)
- action taken
- outcome
  - seriousness criteria
    - causality (i.e. relatedness to trial drug / investigation), in the opinion of the investigator
- whether the event would be considered expected or unexpected.

Assessment of severity, seriousness and causality will be made by the PI or another authorised study doctor. The PI or authorised study doctor will need to decide whether the serious event is an SAE or SAR by assessing whether the event is either unrelated or possibly related to the IMP (causality). If the event is possibly related then it is a SAR and an assessment needs to be made by the Sponsor as to whether the event is expected or not for the IMP. If the SAR is listed in Section 4.8 of the MHRA approved Summary of Product Characteristics then it is expected.

In addition to the PI, the Sponsor will also be required to assess causality and document their assessment on the SAE form. The Sponsor must assess causality after the PI and must confirm that they

have not influenced the PI. The PI's assessment of causality must not be downgraded by the Sponsor.

If an authorised study doctor is unavailable, initial reports without the causality assessment will be submitted to the Sponsor by a healthcare professional within 24hours of becoming aware of the SAE, but will be followed-up by medical assessment as soon as possible thereafter. The PI must always review the SAE form and sign to confirm the contents of the report are accurate and complete and that he/she has also assessed the severity, seriousness and causality of the SAE.

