#### Principal Investigator (PI):

- 1. Checking for AEs and ARs when participants undergo retreatment and at follow-up.
- 2. Using medical judgement in assigning severity, seriousness and causality.

3. Ensuring that all SAEs and SARs are recorded and reported in line with the requirements of the protocol and SUSARs are recorded and reported to the Sponsor within 24 hours of becoming aware of the event and provide further follow-up information as soon as available.

Ensuring that SAEs and SARs (including SUSARs) are chased with Sponsor if a record of receipt is not received within 2 working days of initial reporting.

4. Ensuring that AEs and ARs are recorded and reported in line with the requirements of the protocol.

5. Preparing the clinical sections and final sign off of the Development Safety Update Report (DSUR).

Sponsor:

A medical R&D Director will assess causality and expectedness of behalf of the Sponsor:

1. Clinical oversight of the safety of patients participating in the trial, including an ongoing review of the risk/benefit.

2. Using medical judgement in assessing, causality of SAEs.

3. In order to assess expectedness, the R&D Director will need to check if the SAR is listed in the Reference Safety Information (RSI). If the SAR is listed in the RSI then it is expected. If the event is not listed in the RSI then it is unexpected and is a SUSAR and subject to expedited reporting to the MHRA and REC.

4. Immediate (within 24 hours) review of all SUSARs.

5. Review of specific SAEs and SARs in accordance with the trial risk assessment and protocol as detailed in the Trial Monitoring Plan.

6. Central data collection and verification of AEs, ARs, SAEs, SARs and SUSARs according to the trial protocol.

7. Reporting safety information to the Sponsor Oversight Group for the ongoing assessment of the risk / benefit according to the Trial Monitoring Plan.

8. Expedited reporting of SUSARs to the Competent Authority (MHRA in UK) and REC within required timelines.

9. Notifying Investigators of SUSARs that occur within the trial.

10. Checking for (annually) and notifying the PI of updates to the Reference Safety Information for the trial.

11. Preparing standard tables and other relevant information for the DSUR in collaboration with the PI and ensuring timely submission to the MHRA and REC.

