# Table: Serious adverse event report

Severity Assessed by the Co-I and PI or just PI	The assessment of severity of an SAE will be based on the investigator's clinical judgement using the following definitions: Mild : An event that is easily tolerated by the trial subject, causing minimal discomfort, and not interfering with everyday activities. Moderate: An event that is sufficiently discomforting to interfere with normal everyday activities. Severe: An event that prevents normal everyday activities.
Seriousness Assessed by the Co-I and PI or just PI	An event is considered serious if it meets one or more of the following criteria: (a) results in death (b)life-threatening (c) requires hospitalisation or prolongation of existing hospitalisation (d) results in persistent or significant disability or incapacity (e) consists of a congenital anomaly or birth defect. Important medical events that may not be immediately life- threatening or result in death or hospitalisation but may jeopardise the patient or may require intervention to prevent one of the outcomes listed in the definition above should also be considered serious.

Causality Assessed by the Co-I and PI or just PI	
 
The investigator will assess whether the SAE is likely to be related to the IMP according to the following definitions:
 
Unrelated: Where an event is not considered to be related to the IMP.
 
Possibly related: The nature of the event, the underlying medical condition, concomitant medication, or temporal relationship make it possible that the SAE has a causal relationship to the study drug.
 

Expectedness Assessed by the R&D Director (on behalf of the Sponsor) for single-site trials	To assess expectedness, the R&D Director will need to check if the SAR is listed in the Reference Safety Information (RSI). The RSI for IMPs with a marketing authorization (MA) is section 4.8 (Undesirable Effects) of the MHRA approved Summary of Product Characteristics (SmPC) or for IMPs without an MA, the RSI is the relevant section in the Investigator Brochure (IB). If the SAR is listed in the RSI then it is expected. If the event is not listed in the RSI then it is unexpected and is a SUSAR and subject to expedited reporting to the MHRA and REC.

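### Expectedness of a serious adverse reaction is judged by nature and severity in Sections 9.1 and 9.2 but by listing alone in 9.4 and 9.6, so one unusually severe case of a listed reaction is classified both ways

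*Protocol*

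**What the plan says.** **Nature and severity.** The definitions table in Section 9.1 describes a SUSAR as "A serious adverse reaction, the nature and severity of which is not consistent with the information about the medicinal product in question", the reference being the summary of product characteristics (SmPC) for a marketed product. The operational definitions in Section 9.2 use the same test: "Any SAR that is not expected based on the MHRA SPC for acetazolamide in relation to the nature and severity of the SAR" is to be reported as a SUSAR.

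**Listing alone.** Section 9.4 instructs: "If the SAR is listed in Section 4.8 of the MHRA approved Summary of Product Characteristics then it is expected". Section 9.6, Sponsor item 3, gives the R&D Director the same rule: "If the SAR is listed in the RSI then it is expected". The Expectedness row of the serious adverse event table in 9.6 repeats it, and both places add the converse: "If the event is not listed in the RSI then it is unexpected and is a SUSAR". The table identifies the RSI for a marketed product as Section 4.8 of the SmPC. None of the three places mentions severity.

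**Related provisions.** Severity is rated elsewhere: "Assessment of severity, seriousness and causality will be made by the PI or another authorised study doctor" (Section 9.4). Section 9.4 also treats as a SUSAR any SAR seen in more than 5% of patients and any adverse reaction seen in more than 10%; Section 9.2 states the 5% part. SUSARs are expedited to the MHRA and reported to the REC (9.4, 9.6).

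**The concern.** Expectedness is the step that turns a SAR into a SUSAR and so triggers expedited reporting. If the definition includes severity and the instruction to the person deciding omits it, two assessors can each follow the protocol and classify the same case differently.

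This matters more here than in many trials of a marketed drug. Sections 9.2 and 9.4 give the lack of safety data for acetazolamide with high-dose loop diuretic as the reason for extra vigilance. With a long-established drug, a familiar reaction that takes a worse course than the SmPC describes is one of the signals to look for, and the listing-only rule is blind to it.

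**Working it through.** No sample size, power or event figure underlies this point. The check is a comparison of the rules, followed by a short calculation on the frequency rule.

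**Step 1. The rules side by side**

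| Place | Test of expectedness | Severity used? |
|---|---|---|
| 9.1, SUSAR definition | Nature and severity against the SmPC | Yes |
| 9.2, SUSAR row | Nature and severity against the SPC | Yes |
| 9.4 | Listed in SmPC Section 4.8 | No |
| 9.6, Sponsor item 3 | Listed in the RSI | No |
| 9.6, serious adverse event table | Listed in the RSI | No |

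**Step 2. Apply both tests to the possible cases**

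| Case | 9.1 / 9.2 | 9.4 / 9.6 |
|---|---|---|
| Not listed | SUSAR | SUSAR |
| Listed, severity as described | Expected | Expected |
| Listed, more severe than described | SUSAR | Expected |

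The tests disagree only in the last row.

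**Step 3. Can that row occur?** Yes. One of the SAR entries in Section 9.2 consists of side effects that are listed in the SPC, are intolerable to the patient and lead to investigation. If listed there means listed in Section 4.8, every such SAR is expected under the listing rule by construction, whatever its severity. Only the 9.1 and 9.2 test could make one unexpected.

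**Step 4. Does the severity rating reach the decision?** The investigator's rating is recorded, but the severity row of the table grades an event by its interference with everyday activities, not against the SmPC. No step in 9.4 or 9.6 carries the rating into the expectedness decision.

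**Step 5. Does the 5% rule catch an isolated case?** Share = cases / patients, and it must exceed 5%. The protocol does not state the denominator, so several are shown.

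| Denominator (source) | One case | Two cases |
|---|---|---|
| 27 (maximum acetazolamide arm, 10.1) | 1/27 = 3.7% | 2/27 = 7.4% |
| 20 (half of the planned 40) | 1/20 = 5.0%, not above 5% | 2/20 = 10.0% |
| 40 (planned total) | 1/40 = 2.5% | 2/40 = 5.0%, not above 5% |
| 50 (maximum total) | 1/50 = 2.0% | 2/50 = 4.0% |

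One case exceeds 5% only when the denominator is 19 or fewer (1/19 = 5.3%). That could happen with a running count early in the trial, or if the acetazolamide arm stopped at the minimum of 18 in Section 10.1 (1/18 = 5.6%). At the planned and maximum sizes an isolated case is missed. Repeated cases are caught: from the second case if the denominator is an acetazolamide arm of 20 or 27, and from the third if it is the whole trial (3/40 = 7.5%, 3/50 = 6.0%).

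**The case against.** The best defence is that listing is shorthand for the full definition. Section 9.2 is itself operational and carries severity, so severity does not survive only in a glossary. Section 9.4 requires a full case description, the outcome and a severity assessment, so the assessor has the facts. Nothing says that severity is to be ignored. This reading is possible, but three separate places state the short rule without qualification, and two of them define unexpected as not listed. An assessor who follows them literally leaves severity out.

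The safeguards are also real. Serious events and reactions go to the Sponsor within 24 hours on either branch, the Sponsor keeps an ongoing risk/benefit review (9.6), and the frequency rule catches repeated listed reactions. That narrows the gap to isolated cases but does not close it.

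Three stronger readings are tempting, and the documents do not support them.

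- **Almost any acetazolamide SAR, even a fatal one, would be called expected.** The long side-effect table in Section 8.7 is taken from the British National Formulary. The RSI is SmPC Section 4.8, which is not reproduced, so its coverage cannot be judged. The protocol also has no rule on the expectedness of a fatal outcome.
- **Events are lost from the safety endpoint.** Secondary endpoint 11 (Section 3.5) counts adverse reactions, SARs and SUSARs. A case called expected is still counted as a SAR; only its label changes.
- **The definitions expressly say that a departure in either nature or severity is enough.** The text joins the two with and. That a mismatch in severity suffices is an interpretation, though the natural one: if a listed reaction could never be unexpected through severity, the word would do no work in the definition.

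**Conclusion.** The contradiction stands. A single listed reaction more severe than the SmPC describes is a SUSAR under 9.1 and 9.2, and expected under 9.4 and 9.6. On the second branch it is not expedited to the MHRA and REC on that ground, and at the planned or maximum sample size the frequency rule does not rescue it.

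The size is modest. One type of case is affected, and the consequence is limited to the SUSAR label and onward reporting. Whether such a case will occur cannot be estimated from the documents.

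The conclusion rests on two assumptions: that inconsistency in severity alone makes a reaction unexpected under 9.1 and 9.2, and that listed in 9.4 and 9.6 means what it literally says. It does not depend on what Section 4.8 contains beyond its listing at least one reaction that can occur with greater severity than described.

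**What to change.** Bring Section 9.4, Section 9.6 Sponsor item 3 and the Expectedness row of the serious adverse event table into line with 9.1 and 9.2. In each place state that a SAR is expected only if it is listed in the RSI and its nature and severity are consistent with the RSI, and that a listed term more severe than described is unexpected.

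This is one sentence in three places and uses the protocol's own definition. It changes no treatment, visit, analysis or sample size. The downside is possibly an occasional extra expedited report.

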# TRIAL SUMMARY

Trial Title	Acetazolamide as a chloride sparing Diuretic in patients Admitted with Heart Failure: a pilot study					
Internal ref. no. (or short title)	ADA-HF					
Clinical Phase	Phase II					
Trial Design	Open label, randomised, controlled, pilot and exploratory study.					
Trial Participants	Patients admitted to Castle Hill Hospital with venous congestion due to heart failure who are deemed to require a continuous intravenous infusion (IVI) of furosemide at (10mg/hr) – standard of care for severe venous congestion.					
Planned Sample Size	40 (maximum recruitment of 50)					
Treatment duration	4 days					
Follow up duration	180 days					
Planned Trial Period	30 weeks					
Primary Objective	1) Difference in net fluid loss daily and over a 4 day period					
	2) Difference in serum chloride between baseline and day 4					
Secondary Objective	Differences between the two groups during the 4 day treatment period in:					
	1) daily urine output					
	2) daily weight					
	3) serum electrolyte levels (sodium, bicarbonate and potassium)					
	4) incidence of electrolyte abnormalities; hyponatraemia (<135 mmol/L), hypochloraemia (<96 mmol/L), hypokalaemia (<3.5 mmol/L), high (>30 mmol/L) or low (<22 mmol/L) serum bicarbonate.					
	5) change in renal function measured by serum creatinine (µmol/L) and estimated glomerular filtration rate (eGFR) (ml/min/1.72m2)					
	6) change in urinary electrolyte levels after 48 and 96 hours of treatment; sodium, chloride, potassium.					
	7) clinical assessment of congestion					
	8) ultrasound measures of congestion period; inferior vena cava (IVC) diameter.					
	9) change in breathlessness score using the Likert scale.					
	10) time to clinical euvolaemia and end of intravenous therapy					
	11) length of stay					
	12) rate of adverse events related to acetazolamide – treatment arm only					
	13) rate of adverse events					

Hull University Teaching Hospitals

	NHS T					
	14) Tate of recruitment to study					
	15) time taken to screen & recruit					
	16) rate of drop-out after randomisation – cause specific					
	17) Cause specific hospitalisation or mortality after 30 days and 180 days follow up.					
Investigational Medicinal Product(s)	Acetazolamide					
Formulation, Dose, Route of Administration	Tablet. 250mg twice daily. Oral.					
	Inclusion					
Main inclusion/exclusion	
 
Aged ≥18 of any gender
 
					
criteria	2) Able to give informed written consent to participate in the trial					

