# 3.5 Secondary endpoints/outcomes

All secondary endpoints are exploratory designed to inform future research.

Differences between the two groups during the 4 day treatment period in:

1) daily weight

2) serum electrolyte levels (sodium, bicarbonate and potassium)

3) incidence of electrolyte abnormalities; hyponatraemia (<135 mmol/L), hypochloraemia (<96 mmol/L), hypokalaemia (<3.5 mmol/L), high (>30 mmol/L) or low (<22 mmol/L) serum bicarbonate.

4) change in renal function measured by serum creatinine (µmol/L) and estimated glomerular filtration rate (eGFR) (ml/min/1.72m2)

5) change in urinary electrolyte levels after 48 and 96 hours of treatment; sodium, chloride, potassium.

- 6) clinical assessment of congestion
- 7) ultrasound measures of congestion period; inferior vena cava (IVC) diameter
- 8) change in breathlessness score using the Likert scale.
- 9) time to clinical euvolaemia and end of intravenous therapy

10) length of stay

11) rate of adverse reactions, serious adverse reactions and suspected unexpected serious adverse reactions – treatment arm

- 12) rate of adverse events and serious adverse events both arms
- 13) rate of recruitment to study
- 14) time taken to screen & recruit
- 15) rate of drop-out after randomisation cause specific
- 16) Cause specific hospitalisation or mortality after 30 days and 180 days follow up.

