Any change of condition or other follow-up information should be reported to the Sponsor using the study specific SAE follow-up form, as soon as it becomes available. Events will be followed up until the event has resolved or a final outcome has been reached. The PI is required to assess causality again on the follow-up form. If the PI has a change of opinion on causality after considering the additional follow-up information, the Sponsor will be required to reassess causality and if a SAR, then to assess expectedness.

All SAEs assigned by the PI or authorised study doctor as possibly related to IMP-treatment and those the Sponsor has assessed as unexpected will be classified as SUSARs and will be subject to expedited reporting to the MHRA. The Sponsor will inform the MHRA and the REC of SUSARs within the required expedited reporting timescales.

Additionally, due to the lack of data on the safety and tolerability of acetazolamide in modern patients with heart failure treated with high dose loop diuretic we will consider any SAR that occurs in >5% of patients, and any AR that occurs in >10% of patients as a SUSAR.

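### Section 9.2 sets the serious-reaction limit for hyperchloraemia at the mild band (107-110 mmol/L) instead of >110 mmol/L; as a lesser point, 9.4 gives the SUSAR label on frequency alone

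*Protocol*

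**What the plan says.** **Hyperchloraemia.** The table in Protocol section 9.2 enters chloride 107-110 mmol/L among the adverse reactions. It enters the same band again, with the word severe, among the serious adverse reactions. Section 7.9 calls 107-110 mild and >110 severe, and marks the severe grade as leading to withdrawal if it occurs in the acetazolamide arm. The exclusion criteria, in section 6 and in the Trial Summary, also define severe hyperchloraemia as >110 mmol/L.

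**SUSAR.** Section 9.1 defines a SUSAR as "A serious adverse reaction, the nature and severity of which is not consistent with the information about the medicinal product", meaning the SmPC for a licensed product. Expectedness depends on listing: "If the SAR is listed in Section 4.8 of the MHRA approved Summary of Product Characteristics then it is expected" (9.4), and "If the SAR is listed in the RSI then it is expected" (9.6, sponsor duties). Section 9.4 then adds a frequency rule under which the trial will treat "any SAR that occurs in >5% of patients, and any AR that occurs in >10% of patients as a SUSAR". Section 9.2 gives only the first half: "we will consider any SAR that occurs in >5% of patients as a SUSAR". Secondary endpoint 11 in section 3.5 is the "rate of adverse reactions, serious adverse reactions and suspected unexpected serious adverse reactions – treatment arm".

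**The concern.** The SAR tier for chloride is set at the wrong band. A mild rise falls into two classes at once, and the graver class brings a report to the sponsor within 24 hours (9.4). A rise above 110 mmol/L, the one that ends treatment in the acetazolamide arm, is in neither listed class. The SAR rate in endpoint 11 would then include mild laboratory changes and could leave out severe ones. This laboratory value matters here: the trial tests whether acetazolamide raises chloride, and patients may enter with chloride up to 110.

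The frequency rule is a smaller matter of labelling. Under 9.1 a non-serious reaction cannot be a SUSAR however common it is, yet 9.4 makes it one above 10%. SUSAR status brings sponsor review within 24 hours (9.6) and expedited reports to the MHRA and REC (9.4, 9.10). The SUSAR count in endpoint 11 would mix unexpected serious reactions with frequent non-serious ones. Staff working from 9.2 and staff working from 9.4 would also class the same AR differently.

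**Working it through.** There is no stated figure to reproduce. The check sets the limits side by side and then counts.

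**1. Chloride limits (mmol/L)**

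| Place | 107-110 | >110 |
|---|---|---|
| 9.2, AR list | AR | not listed |
| 9.2, SAR list | SAR, severe | not listed |
| 7.9 | mild, no automatic withdrawal | severe, withdrawal in acetazolamide arm |
| Section 6 and Trial Summary exclusions | not severe | severe |

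Outside the SAR list, each place that grades severity puts severe at >110. The SAR row is the odd one out, and it repeats the AR band exactly.

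**2. Is an AR in 9.2 non-serious?** Bicarbonate shows the two tiers: <23 mmol/L is an AR and <20 is a SAR. Values from 20 to below 23 (20, 21 or 22 if reported as whole numbers) are therefore ARs and not SARs. By the protocol's own tiers they are non-serious and cannot meet 9.1, but the AR part of the 9.4 rule can make them SUSARs.

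**3. Triggering counts.** The smallest count k with k/n above the threshold is floor(n × threshold) + 1.

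| Denominator n | SAR >5% | AR >10% | Check |
|---|---|---|---|
| 1-9 acetazolamide patients | 1 | 1 | 1/9 = 11.1% |
| 10-19 | 1 | 2 | 1/19 = 5.3%; 1/10 = 10.0% does not exceed; 2/19 = 10.5% |
| 20-29 | 2 | 3 | 1/20 = 5.0% and 2/20 = 10.0% do not exceed; 2/27 = 7.4%; 3/27 = 11.1% |
| all 40 | 3 | 5 | 2/40 = 5.0% and 4/40 = 10.0% do not exceed; 3/40 = 7.5%; 5/40 = 12.5% |
| all 50 | 3 | 6 | 2/50 = 4.0%; 5/50 = 10.0% does not exceed; 3/50 = 6.0%; 6/50 = 12.0% |

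The 20-29 row covers half of 40 (20), half of 50 (25) and the 27 given for the acetazolamide arm in section 10.1. The first two rows matter only if the rule is applied as patients accrue; the protocol does not say when it is assessed.

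**4. Which denominator?** Both statements of the rule say only patients. In favour of acetazolamide-treated patients are the AR definition ("An untoward and unintended response in a participant to an investigational medicinal product which is related to any dose administered to that participant"), the Trial Summary objective ("rate of adverse events related to acetazolamide – treatment arm only") and endpoint 11. Against it, 9.5 starts the AR, SAR and SUSAR reporting period at the first IMP dose whichever arm the patient is in, so an all-patient denominator remains arguable. Both are therefore shown.

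**5. The two faults together.** With 20-29 acetazolamide patients, two related rises to 107-110, classed as SARs because of the misplaced limit, exceed 5% and become a SUSAR under both 9.2 and 9.4. With the chloride limit corrected, it would take three, as ARs, and only under 9.4.

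**6. Plausibility.** Section 2.2 gives side effects in 5-10% of patients at doses up to 500 mg per day. Assume that one single reaction has that rate. The chance of 3 or more, P(X ≥ 3) with X ~ Binomial(n, p), is 0.075 (p = 5%) to 0.323 (p = 10%) for n = 20, and 0.150 to 0.515 for n = 27.

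**The case against.** The best defence is that the frequency rule is a considered choice. Section 9.4 presents it as an addition, gives the lack of modern safety data as its reason, and errs towards over-reporting. A reader might infer that the sponsor has confused the definition or that real SUSARs would be missed. The documents do not support this: unlisted serious reactions are still identified through 9.1, 9.4 and 9.6. The 9.2 entry is a table row about SARs, and 9.4 can be read as the fuller statement. This defence stands, and it reduces the point to the label, the differing wording and the denominator.

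A reader might also take the bicarbonate example as proof that an expected reaction is being called unexpected. It does not go that far. Section 2.2 takes metabolic acidosis from the British National Formulary, while expectedness depends on SmPC section 4.8, which is not at hand. The example shows only that the reaction is non-serious.

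On chloride, it can be said that this is a slip in one cell, that the right limit appears elsewhere, and that no patient is left unprotected. A reader might infer that values >110 would go unrecorded or unmanaged. They would not: 7.9 requires withdrawal in the acetazolamide arm, 9.3 has clinically significant laboratory values recorded, and an investigator could still judge seriousness under 9.1. The fault is misclassification, with no missed safety action. It remains an operative limit that contradicts the rest of the protocol, and no stated intent explains it.

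**Conclusion.** The chloride limit in 9.2 is wrong as written and should be corrected. Mild rises of 107-110 mmol/L count as SARs, and rises >110 have no listed class. This rests on comparing text within one protocol and needs no outside assumption.

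The SUSAR label is a minor inconsistency. The AR part contradicts the seriousness requirement in 9.1; both parts set aside the listing test for expectedness; and 9.2 lacks the AR part. Its size depends on the unstated denominator: 2 SARs or 3 ARs with 20-29 acetazolamide patients, 3 or 5 among 40, 3 or 6 among 50. The probabilities rest on applying an overall side-effect range to a single reaction and on the acetazolamide denominator.

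The practical effect is limited. SARs already reach the sponsor within 24 hours, the secondary endpoints are exploratory, and conventional counts can be rebuilt from the recorded ARs and SARs. Because serum chloride is a co-primary endpoint, a reader might infer that the wrong limit biases it. It does not: that endpoint is the measured change from day 1 to day 4, and the class given to a reaction in 9.2 does not enter it. Net fluid loss is likewise unaffected.

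**What to change.** 1. In 9.2, set the SAR limit for hyperchloraemia to >110 mmol/L and keep 107-110 mmol/L as the AR, in line with 7.9 and the exclusion criteria.
2. Keep SUSAR as defined in 9.1. Rename the rule a frequency-based safety report: the same SAR in >5%, or the same AR in >10%, of a stated denominator. Patients who have received acetazolamide are the natural choice. Use identical wording in 9.2 and 9.4.
3. Say when the rule is assessed. If it runs as patients accrue, a single AR among the first 9 dosed, or a single SAR among the first 19, triggers it; the sponsor should accept that knowingly or set a minimum number dosed.
4. Leave these reports out of the SUSAR count in endpoint 11. The sponsor may keep the expedited timelines for them.

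The cost is a protocol amendment to safety wording and one laboratory limit, possibly a substantial one needing MHRA and REC submission. It needs no new data, visits or committee. If the expedited timelines are kept, no reporting is lost; if they are dropped, frequent listed reactions would no longer be expedited automatically, and the sponsor must weigh that trade-off.
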